#### 1.11 Sample size calculation

Based on the pooled data from the CAIN457A program (CAIN4572302 and CAIN4572303), the PASI 90 response rate for biologics-naïve patients treated with AIN457 300 mg s.c. was 74.3% at 24 weeks. Of those who were PASI 90 responders at Week 24, 81.8% of patients maintained their PASI 90 response until Week 52.

It was assumed that a dosing frequency of 6 weeks (Group 2) will differ in PASI 90 response up to 7% worse compared a dosing frequency of 4 weeks (Group 1). This assumption of a difference of maximally 7% is based on simulation of the PK levels obtained with maintenance treatments of AIN457 300 mg every 6 weeks and the correlation between plasma levels and the clinical response seen in the AIN457 Phase 3 studies.

A total of 554 patients per group are required to achieve 90% power on a one-sided, 2.5% significance level to demonstrate the non-inferiority of 6-weekly vs. 4-weekly dosing, if the true maintenance rates are 81.8% under 4-weekly and 74.8% under 6-weekly dosing and the non-inferiority margin is predefined as -15%.

The response rates underlying this estimation were obtained from pooled data of studies analyzed according to the ITT-principle using the same algorithm to handle drop-outs or protocol violations as in this present study. Therefore, the effect of drop-outs or protocol violations should be already accounted for in the effect estimates and no further adjustments of the sample size are required. However, to account for the fact that there might be minor differences (e.g. with respect to drop-out rates) between the historical data and the data to be observed in this study, the sample size was rounded up slightly to 570 patients/group who were to be randomized to Group 1 or Group 2 (giving a total of 1140 patients in both groups) of this study.

Assuming a PASI 90 response rate of 74% at Week 24, 1580 patients were to be enrolled at baseline in this study in order to achieve the required sample size for randomization at Week 24. This number still allows for some drop-out patients or patients withdrawing consent at or after randomization even after experiencing a PASI 90 response.

### 1.12 Interim analyses

No interim analysis was planned or performed for this study.

## 2 Clinical Study Report -Appendix 16.1.9 Documentation of statistical methods

If not otherwise specified, p-values will be presented as two-sided p-values, and two-sided confidence intervals will be displayed. For all tests the level of significance will be set to 5%.

## 2.1 Analysis of continuous data

#### 2.1.1 Summary statistics for continuous data

The following summary statistics will be provided for continuous data by visit and dosing group (if applicable): N, mean, standard deviation, minimum, median, maximum.

#### 2.1.2 Analysis of variance/covariance

Analysis of covariance (ANCOVA) will be used with dosing group, country and body weight stratum as explanatory variables and baseline value as covariate. In general, SAS Type III sums of squares will be utilized.

Difference between dosing groups will be determined using least-square means (LSMs) and t-tests using the pooled error term from the linear model. 95% percent CIs for the treatment difference will be calculated based on differences in LSM estimates.

## 2.2 Analysis of binary (and categorical) data

#### 2.2.1 Summary statistics for binary and categorical data

Summary statistics for discrete variables will be presented in contingency tables and will include absolute and relative frequencies. If applicable, risk differences will be calculated

with a corresponding two-sided 95%-CI (asymptotic Wald CIs with continuity correction) using the SAS PROC FREQ procedure with the RISKDIFFC option.

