5.3.1 IRT Stratification

Randomization will be stratified at the Week 24 visit (Randomization) by body weight. This stratification ensures balanced allocation of patients to treatment groups within the weight strata. The strata will be "body weight $\geq 90~\text{kg}$ " or "body weight < 90~kg." All treatment groups will be stratified by body weight assessed at Week 24. The randomization scheme for patients will be reviewed and approved by a randomization expert.

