#### Version 1.1

- Inclusion of PP-FUS analysis set for the analysis of rebound and relapse
- Removal of indirect response model for PK analysis
- Removal of confidence intervals for risk differences of PASI responder rates
- Inclusion of analysis of AEs of special interest

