#### 1.8.4 Supportive analyses

Sensitivity analyses for the primary outcome will be performed as follows:

- (A) In addition to the logistic regression model the risk difference for PASI 90 response at Week 52 between Group 1 and Group 2 will be computed with the corresponding 95%-CI (asymptotic Wald CIs with continuity correction) using the SAS PROC FREQ procedure with the RISKDIFFC option.
- (B) The primary analysis (logistic regression analysis) and the analysis of risk difference will be repeated for the PP-P90R set.
- (C) An analysis based on multiple imputations of the PASI 90 response at Week 52 will be performed. Details are described in Section 2.2.3.

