# PASI 50/75/90/100 and IGA mod 2011 0 or 1 response over time in Treatment Period 2 and Follow-Up Period

Summary statistics for PASI 50/75/90/100 response and for IGA mod 2011 0 or 1 response from Week 24 to Week 52 will be presented for the FAS-P90R and the FAS-P75R separately in contingency tables including absolute and relative frequencies. For the FAS-P75R also the response rates at Week 60 will be provided. Risk differences between the dosing groups will also be provided.

Figures will be provided as well displaying estimates for responder rates by dosing group.

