#### PASI score over time in Treatment Period 2 and Follow-Up Period

Summary statistics will be provided for absolute PASI scores as well as for absolute and percent change from baseline by visit and treatment group. The analysis will be performed until Week 52 in the FAS-P90R and until Week 60 for the FAS-P75R. Figures for mean course of the PASI score will also be provided.

The absolute PASI score will be analyzed by analysis of covariance (ANCOVA) models with dosing group, country and body weight stratum as explanatory variables and baseline value as covariate. ANCOVAs will be performed at each visit starting with Week 28.

## DLQI, EQ-5D, WPAI-PSO and assessment of pain, itching and scaling in Treatment Period 2

For the DLQI subscale and the DLQI total score, the EQ-5D VAS and the EQ-5D utility index, for each of the main outcomes of the WPAI-PSO and for the assessment of pain, itching and scaling, the absolute and percentage change from baseline to each visit during

Treatment Period 2 where the scales are assessed will be derived. Summary statistics will be provided for absolute values as well as for the percentage change by visit and dosing group.

Page 32

ANCOVA models with dosing group, country and body weight stratum as explanatory variables and baseline value as covariate will be performed for the visits Week 36, 48 and 52.

In addition, summary statistics will be provided for number of subjects achieving DLQI 0 or 1 at each visit where the DLQI is assessed. Risk differences including 95%-CIs will also be presented for the visits Week 36, 48 and 52.

For the single EQ-5D dimensions contingency tables will be provided for each visit where the scale was to be assessed. Changes from baseline to each visit will be displayed using the categories improved, unchanged and worsened in each dimension.

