#### Relapse and Rebound at Week 60

Contingency tables including absolute and relative frequencies will be provided for relapse and rebound at Week 60 in the FUS and in the PP-FUS. Risk differences including 95%-CIs between the (former) dosing groups, i.e. Group 3 vs. Group 4, will also be presented.

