#### Crude incidence and 100\*(1-α)% confidence interval 2.2.4

For n subjects, each at risk to experience a certain event with probability  $\pi$ , the crude incidence is estimated as p=x/n, where x is the number of subjects with the event.

Absolute and relative frequencies will be displayed as well as 95% confidence interval for the relative frequency based on the score method including continuity correction (Newcombe 1998).

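### The planned Wald interval for risk differences is much too narrow when events are very rare, which could affect the Week 60 rebound comparison of Groups 3 and 4

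*SAP*

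**What the plan says.** SAP 2.2.1 states that, where applicable, risk differences are calculated "with a corresponding two-sided 95%-CI (asymptotic Wald CIs with continuity correction) using the SAS PROC FREQ procedure with the RISKDIFFC option". SAP 1.8.4(A) names the same method for the supportive analysis of the primary endpoint.

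For the Week 60 outcomes SAP 1.8.8 adds: "Risk differences including 95%-CIs between the (former) dosing groups, i.e. Group 3 vs. Group 4, will also be presented". This is done in the FUS and the PP-FUS. SAP Table 1-6 classes relapse and rebound as additional exploratory variables.

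For a single proportion the SAP chooses differently. Section 2.2.4 gives the "95% confidence interval for the relative frequency based on the score method including continuity correction".

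SAP 1.8.7 is uneven about intervals. For PASI 50/75/90/100 and IGA 0/1 response it says only: "Risk differences between the dosing groups will also be provided". For DLQI 0 or 1 it says: "Risk differences including 95%-CIs will also be presented for the visits Week 36, 48 and 52". The document history for version 1.1 records: "Removal of confidence intervals for risk differences of PASI responder rates". IGA is not mentioned there.

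On randomisation, Protocol 5.3.1 says: "All treatment groups will be stratified by body weight assessed at Week 24". No risk difference in the SAP is stratified.

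**The concern.** The Wald standard error is estimated from the observed proportions, so an arm with no events contributes nothing to it. If neither arm has an event, the standard error is zero and only the continuity term is left.

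Rebound could produce such tables. It requires PASI at or above 125% of Baseline, or a new or more inflammatory form of psoriasis, in patients who had at least a PASI 75 response at Week 24. Protocol 3.3 notes that the 2-weekly regimen has not been studied in a maintenance period, and Protocol 3.1 sets Week 60 as the visit at which relapse and rebound are explored. A printed difference of 0 with limits of ±0.95 points would suggest that an excess of more than 1 point had been ruled out, when the data allow about 3.5 points.

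**Working it through.** **Inputs.** Protocol 9.7.1 expects 13.3% of 1580 patients in Groups 3 and 4: 0.133 × 1580 = 210, or 105 per arm. This is an upper limit for the FUS, since only patients entering follow-up count. The documents give no rebound or relapse rate, so the true rates below are assumptions.

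**The plan's own figure.** Protocol 9.7.1 claims more than 90% power for 4% vs 18% with 105 per arm, two-sided 5%. With mean rate 0.11:
- null SE = √(2 × 0.11 × 0.89/105) = 0.0432
- alternative SE = √((0.04 × 0.96 + 0.18 × 0.82)/105) = 0.0421
- z = (0.14 − 1.96 × 0.0432)/0.0421 = 1.315, so power is 90.6%.

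The figure reproduces. The documents state no width or coverage for any risk-difference interval.

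**Formulas**, with d = p1 − p2:
- Planned: d ± {1.96 √[p1(1−p1)/n1 + p2(1−p2)/n2] + (1/n1 + 1/n2)/2}.
- Newcombe, from the Wilson limits l and u of each arm: d − √[(p1−l1)² + (u2−p2)²] to d + √[(u1−p1)² + (p2−l2)²].

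**No events in either arm, 105 per arm.** Planned: 0 ± (0 + 1/105) = ±0.95 points. The Wilson upper limit for 0/105 is 3.84/(105 + 3.84) = 3.53%, so Newcombe gives ±3.53 points. Miettinen-Nurminen gives ±3.55. The exact 97.5% upper limit for one arm is 1 − 0.025^(1/105) = 3.45%. With 90 per arm the planned interval is ±1.11 and Newcombe ±4.09.

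**Other tables, 105 per arm, in percentage points:**

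| Events | Planned | Newcombe |
|---|---|---|
| 0 vs 1 | −3.76 to 1.86 | −5.20 to 2.66 |
| 1 vs 1 | ±3.58 | ±4.32 |
| 3 vs 3 | ±5.46 | ±5.54 |
| 4 vs 19 | −23.46 to −5.11 | −23.04 to −5.95 |

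**Exact coverage** of the planned interval, summing over all binomial outcomes, 105 per arm:

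| True rates | Coverage |
|---|---|
| 0% vs 1% | 65% |
| 0% vs 1.5% | 80% |
| 0% vs 2% | 88% |
| 0.5% vs 2% | 92.7% |
| 0% vs 3% | 95.9% |
| 0% vs 4% | 92.5% |
| 0% vs 5% | 96.8% |
| 1% vs 3% | 95.7% |
| 1% vs 1% | 99.9% |
| 2% vs 2% | 99.5% |

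The low values can be checked by hand. At 0% vs 2% the chance of no events is 0.98^105 = 0.120. The interval is then ±0.95 and misses the true 2 points, so coverage is about 1 − 0.120 = 88%. At 0% vs 1% the chance is 0.99^105 = 0.348, which gives 65%. At 0% vs 4% the 0-event and 1-event tables both miss (the latter stops at 3.76): 0.96^105 + 105 × 0.04 × 0.96^104 = 0.014 + 0.060 = 0.074. Newcombe covers above 99% at 0% vs 1% and at 0% vs 2%.

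**Commoner outcomes.** For PASI 90 at 3.8% vs 18% (105 per arm) the planned interval covers 96.7%, Newcombe 95.6%. For the primary endpoint at 81.8% vs 74.8% (570 per arm) the planned interval covers 95.7%.

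**Weight strata.** With 570 per arm and response assumed to differ by 5 to 20 points between weight strata, the unstratified SE is 0.2% to 3.1% larger than the stratified one (at most 0.02433 vs 0.02360).

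**The case against.** The under-coverage depends on rates that the documents do not supply. It needs unequal rates with one arm at or near zero, and it moves in jumps. With 80 per arm, for example, coverage at 0% vs 1% is 100%, because the no-event limit of 1/80 = 1.25 points then contains the true difference; at 0% vs 2% it is 80%. Rebound is a composite, so a near-zero rate cannot be taken for granted. It is exploratory, has no hypothesis or decision rule, and is tabulated with counts, so a reader would see 0/105 against 0/105. All of this stands, and it limits the point to sparse tables. It does not rescue an interval of ±0.95 points from two empty cells.

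Three stronger readings are tempting, and the documents do not support them:
- A reader might infer that every risk difference is reported too precisely, including PASI 90 in Group 3, where 3.8% is planned. The continuity correction prevents that: for 4 vs 19 events the planned interval is wider than Newcombe (18.4 vs 17.1 points), and by 3 events per arm the two nearly agree.
- A reader might infer that leaving out the weight strata makes the intervals invalid. It makes them very slightly wide. Both confirmatory logistic models adjust for weight, and Protocol 9.4.5 asks for the raw, unadjusted difference as a supportive analysis.
- A reader might take the missing PASI intervals for an oversight. The document history records their removal as a choice. What stays unclear is IGA, and how SAP 1.8.7 fits the general rule in 2.2.1.

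**Conclusion.** The point holds for very sparse tables only: about 0 to 2 events in total, or one arm at or near zero. With no events at 105 per arm, the planned interval is about 3.7 times too narrow against the score interval (3.53/0.95). Coverage falls to between 65% and 93% over assumed rates from 0% vs 1% to 0.5% vs 2%. From 0% vs 3% upward it is mostly at or above 95%, with a dip to 92.5% at 0% vs 4%; at equal rates of 1% to 2% it is 99.5% or more. If rebound or relapse turns out to be common, the choice of interval hardly matters.

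The rule is adequate or slightly conservative for PASI 90 and for the primary-endpoint difference. The non-inferiority decision rests on the odds-ratio interval and the key secondary decision on the logistic Wald test (SAP 1.8.6), so neither changes. The matter is still worth correcting, because a plausible rebound result would be printed with misleading limits.

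**What to change.** In SAP 2.2.1, at least for rebound and relapse in 1.8.8, replace the continuity-corrected Wald interval with a Newcombe or Miettinen-Nurminen score interval for the difference. This matches the score method in SAP 2.2.4 and needs a different option in the same procedure plus a sentence of text. The cost is wider intervals when events are very rare.

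Two optional additions:
- Stratify the responder risk differences by Week 24 weight, for consistency with the randomisation and for a small gain in precision.
- State in SAP 1.8.7 whether the PASI and IGA differences carry confidence intervals, so that it agrees with 2.2.1.

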#### 2.2.2 Logistic regression

The analysis of the primary endpoint and of the key secondary endpoint will be performed using logistic regression models with factors dosing group, country and body weight at Week 24 (<90 kg or ≥90 kg). Potential further covariates in the model are specified in Section 1.8.2 and Section 1.8.5. Odds ratios will be computed for comparisons of secukinumab dosing regimens utilizing the logistic regression model fitted.

The odds ratios and their two-sided 95%-Wald confidence intervals will be computed utilizing the logistic regression model fitted. P-values will be given according to the descriptions in Section 1.8.2 and Section 1.8.5.

In case of subgroup analyses where the grouping variable is one of the above described factors in the logistic regression model the respective factor is excluded from the model.

The SAS procedure PROC LOGISTIC will be used for calculating logistic regression models. Dummy-coding will be performed with treatment reference category being 300 mg secukinumab every 4 weeks.

If the logistic regression model does not converge the following steps will be performed:

- 1. Run the PROC LOGISTIC procedure with EXACT statement;
- 2. If convergence not reached, remove the covariates from the model one by one until convergence is reached; start with removing country, followed by weight stratum and PASI 90 response at Week 16
- 3. If convergence not reached, perform Fisher's exact test.

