#### 1.8.2 Statistical hypothesis, model, and method of analysis

The statistical null-hypothesis to be rejected in the primary analysis is that the odds ratio of maintaining a PASI 90 response for patients with secukinumab 4-weekly dosing versus patients on secukinumab 6-weekly dosing exceeds the non-inferiority margin of  $1+\delta$ .

The primary hypothesis is stated as follows:

Let  $\pi_j$  denote the probability of a PASI 90 response at Week 52 for dosing group j, j=0, 1, where

- 0 corresponds to 4-weekly dosing
- 1 corresponds to 6-weekly dosing

The following hypothesis will be tested

$$H_{01}$$
:  $(\pi_0 / (1 - \pi_0)) / (\pi_1 / (1 - \pi_1)) \ge 1 + \delta$  versus  $H_{A1}$ :  $(\pi_0 / (1 - \pi_0)) / (\pi_1 / (1 - \pi_1)) < 1 + \delta$ 

The non-inferiority margin  $1+\delta$  is calculated as 2.23 assuming a PASI 90 response maintenance rate of 81.8% under 4-weekly dosing treatment scheme and using a 15% non-inferiority margin. The **primary analyses** will be performed comparing dosing groups (Group 1 vs. Group 2) with respect to the primary efficacy variable in a logistic regression model with the factors dosing group, country, PASI 90 response at Week 16 (Yes, No) and body weight at Week 24 (< 90 kg or  $\geq$  90 kg, for model definition see Section 2.2.2). The odds ratios and their two-sided 95%-Wald confidence intervals (CIs) will be given.

In case of subgroup analyses where the grouping variable is one of the above described factors in the logistic regression model the respective factor is excluded from the model.

Additionally, the one-sided p-value for the shifted null-hypothesis will be given. The respective test statistic is calculated as

$$\frac{\hat{\beta}-\beta_0}{se_{\hat{\beta}}}$$

where  $\hat{\beta}$  is the type 3 maximum likelihood estimate of the dosing group parameter in the logistic regression model and  $se_{\hat{\beta}}$  is its standard error.  $\beta_0$  is the non-inferiority margin of the estimator which corresponds to the  $\delta$  from the above null-hypothesis and is therefore set to  $ln(1+\delta) = ln(2.23) = 0.80$ .

Only in case that the number of patients with response (or non-response) in one of the groups is 5 or lower, exact logistic regression will be used for the primary analysis instead of logistic regression using maximum-likelihood based estimators.

The primary analysis set will be the FAS-P90R.

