### 1.8.6 Testing strategy of the primary and the key secondary analysis

**Significance Level:** The primary analysis will be performed at the one-sided 2.5% level which corresponds to a two sided 5% level. Non-inferiority of 6-weekly vs. 4-weekly dosing will be claimed, if the upper limit of the two sided 95%-Wald CI for the odds ratio estimated in the above described logistic regression model does not exceed 2.23. The key secondary analysis will be performed on the two-sided 5% level of significance. The test decision will be based on the Wald test, i.e. if the p-value from the test is below 0.05.

**Multiplicity issues:** The key secondary analysis will be included in the confirmatory testing strategy using a hierarchical testing strategy. The key secondary hypothesis will be a priori ordered below the primary hypothesis. This means that no multiplicity adjustment of the significance level is required; however, confirmatory evidence will be claimed only if non-inferiority with regard to the primary endpoint has been successfully demonstrated before. Otherwise, the result for the secondary endpoint will be interpreted as being purely explorative, independent of the nominal p-value.

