#### Programming notes:

- The SAS procedure MIANALYZE expects a variable called " IMPUTATION which is generated by the MI procedure. It might be needed to set the SAS option "VALIDVARNAME=UPCASE" temporarily in the program before the MI call, this option should be reset after the MIANALYZE call to VALIDVARNAME=V6.
- In case there are no missings in one dosing group, the MI procedure does not impute any values. In this case the corresponding data need to be imputed manually outside PROC MI and added to the dataset <impdata>.

The imputed data are saved in data set <impdata>. The outcome of interest, i.e. the PASI 90 response will be calculated as follows:

```
DATA <impdata2>;
SET <impdata>;
IF <change from baseline PASI week primary endpoint>/<baseline PASI> >=0.90 THEN <PASI 90
response> =1;
ELSE <PASI 90 response>=0;
RUN;
```

The treatment differences for each imputed data set will then be evaluated by means of logistic regression models as described in Section 2.2.2. This analysis will be done by **Novartis** 

IMPUTATION for the comparison to the control group. A data set containing the estimated parameters of the logistic regression will be created (ods output ParameterEstimes=Igsparms).

The estimates based on the 50 imputed data are then combined by applying Rubin's rules for multiple imputed data sets, see Little and Rubin (2002). For this estimation the SAS procedure MIANALYZE will be used (parms=Igsparms, modeleffects <Treatment group>). ODS OUTPUT data sets containing ParameterEstimates, VarianceInfo and ModelInfo will be produced.

The data set ParameterEstimates contains the estimate for the log(odds ratio) and the lower and upper confidence intervals. These three variables will be back-transformed and presented in the results.

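### The SAP tests the dosing-group parameter against +ln(2.23), but with 4-weekly dosing as reference and PASI 90 response as the event that parameter has the opposite sign, and the model's event and contrast are not stated

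*SAP*

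**What the plan says.** SAP 1.8.2 states the primary hypothesis on the "odds ratio of maintaining a PASI 90 response for patients with secukinumab 4-weekly dosing versus patients on secukinumab 6-weekly dosing". The null is that this ratio is at least 1+δ = 2.23; the alternative is that it is smaller. Protocol 9.4.2 and 9.4.3 say the same.

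The test statistic in SAP 1.8.2 is (β̂ − β0)/se. β̂ is the "maximum likelihood estimate of the dosing group parameter in the logistic regression model", and β0 is set to ln(2.23) = 0.80. For the model definition the section refers to SAP 2.2.2, which serves both the primary and the key secondary model and says: "Dummy-coding will be performed with treatment reference category being 300 mg secukinumab every 4 weeks".

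SAP 1.8.6 allows the non-inferiority claim on this condition: "upper limit of the two sided 95%-Wald CI for the odds ratio estimated in the above described logistic regression model does not exceed 2.23". SAP 1.8.4 adds "The primary analysis (logistic regression analysis) and the analysis of risk difference will be repeated for the PP-P90R set", as well as a multiple-imputation analysis. For the latter, SAP 2.2.3 codes response as 1, compares with the control group and reads the result from the parameter estimates: "The data set ParameterEstimates contains the estimate for the log(odds ratio) and the lower and upper confidence intervals". These values are then back-transformed, with no inversion mentioned.

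**The concern.** The statistic and the coding rule describe the same parameter with opposite signs if response is the event. That is the natural choice, because π in the hypothesis is a response probability. A margin of +0.80 belongs to the 4-weekly over 6-weekly log odds ratio. Dummy coding with 4-weekly as reference delivers the 6-weekly over 4-weekly log odds ratio, whose margin would be −0.80.

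This is the trial's only confirmatory non-inferiority test, and under SAP 1.8.6 it also decides whether the key secondary result can be confirmatory. With the wrong sign, the statistic favours non-inferiority more strongly the worse 6-weekly dosing performs. An upper limit of 2.23 read on that same inverted odds ratio behaves in the same way.

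**Working it through.** **Inputs.** 4-weekly maintenance rate 81.8%, margin 15 points, 570 per group, one-sided 2.5% (SAP 1.8.2, 1.8.6, 1.11). The calculations are unadjusted unless stated, because the documents give no covariate effects.

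**1. The plan's own margin.** (0.818/0.182)/(0.668/0.332) = 2.234, which the SAP gives as 2.23; ln(2.23) = 0.802, given as 0.80. Both reproduce, so the issue is sign only.

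**2. What each coding returns with 4-weekly as reference.**

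| Modelled event | Primary model | Key secondary model |
|---|---|---|
| Ratio stated in the SAP | 4w/6w | 2w/4w |
| Response | 6w/4w (inverted) | 2w/4w (matches) |
| Non-response | equals 4w/6w of response (matches) | equals 4w/2w of response (inverted) |

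Under this one reference category, no event choice gives both stated ratios directly. One of them always needs an inversion or contrast that the SAP does not mention.

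**3. The literal statistic at the margin** (observed 81.8% and 66.8%, response as event).
- β̂ = ln[(0.668/0.332)/(0.818/0.182)] = −0.804
- se = √[1/(570×0.818×0.182) + 1/(570×0.668×0.332)] = 0.140
- Literal: (−0.804 − 0.802)/0.140 = −11.4. OR(6w/4w) = 0.448, 95% CI 0.340 to 0.589, so the upper limit is far below 2.23.
- Hypothesis direction: (+0.804 − 0.802)/0.140 = +0.01. OR(4w/6w) = 2.234, 95% CI 1.697 to 2.941, so there is no claim.

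**4. Probability of claiming non-inferiority.** Exact sum over all pairs of binomial counts, Wald interval on the log odds ratio, 4-weekly rate 81.8%.

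| True 6-weekly rate | Literal reading | Hypothesis direction |
|---|---|---|
| 66.8% (margin) | 1.000 | 0.0246 |
| 70% | 1.000 | 0.178 |
| 74.8% (planning rate) | 1.000 | 0.753 |
| 81.8% | 0.999 | 0.999 |
| 87.8% | 0.50 | 1.000 |

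The literal reading starts to fail only when 6-weekly dosing is clearly better. Modelling non-response with 4-weekly as reference reproduces the last column, and so does option (b) in the fix.

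**5. Adjusted check.** 3,000 simulated trials at a conditional OR(4w/6w) of 2.23. The covariates are assumed: ten equal countries with log-odds SD 0.2; 45% at or above 90 kg, log OR −0.5; 85% Week 16 PASI 90 responders, log OR +1.2. The claim rate is 1.000 on the literal reading and 0.023 in the hypothesis direction (Monte Carlo SE 0.003).

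**6. Would it be noticed?** At 66.8%, the continuity-corrected Wald interval for the risk difference (SAP 1.8.4) excludes −15 points in 2.1% of trials. A literal claim would therefore conflict with it in 97.9%. At the observed rates in step 3 that interval is −20.2% to −9.8%.

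**7. Key secondary.** At 18% against 4% with 105 per group, the odds ratio is (0.18/0.82)/(0.04/0.96) = 5.27, or 0.19 if inverted. Wald z is +2.97 or −2.97, and the two-sided p is 0.00296 either way.

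**The case against.** The strongest reply is that the SAP already fixes the direction. The hypothesis names the response and the 4-weekly over 6-weekly ratio. The alternative (ratio below 1+δ) implies a lower-tail test. β0 "is the non-inferiority margin of the estimator which corresponds to the" δ of that null hypothesis, so the estimator ought to be the one for the same ratio. SAP 2.2.2 also hands the test back: "P-values will be given according to the descriptions in Section 1.8.2 and Section 1.8.5". A reference category is only a parameterisation, and 2.23 makes sense as an upper bound only for 4-weekly over 6-weekly.

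Most of this stands. It would be wrong to say that the SAP never gives an event, contrast or tail: the hypothesis gives the response and the contrast, and the tail follows from them. An analyst who reports the 4-weekly versus 6-weekly contrast, or models non-response, satisfies the primary text and runs a valid test.

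It does not close the gap. The statistic uses the dosing-group parameter itself, not a contrast derived from it, and the only text defining that parameter points the other way when response is modelled. Reaching the hypothesis direction requires an event level, contrast or inversion that the SAP does not state. SAP 1.8.6 repeats the 2.23 limit without naming a direction. The risk difference would usually reveal a mistake, but it is supportive and does not decide the claim.

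**Conclusion.** The point holds as a fault in specification: the SAP does not correctly link the fitted parameter to the odds ratio in its own hypothesis. The hypothesis, the margin and the protocol are correct.

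The size is conditional. If the coding sentence and the statistic are applied literally with response as the event, the chance of a false claim at the margin is about 100% instead of about 2.5% (570 per group, 4-weekly rate 81.8%, unadjusted; the adjusted simulation under assumed covariate effects agrees).

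A reader might infer that the trial's type I error is 100%, or that the analysis was run backwards. The documents support neither. The first figure belongs to one reading, which the stated hypothesis contradicts; the second would need the programs or results, which are not part of the plan. The key secondary p-value is untouched. The multiple-imputation section carries no 2.23 rule, so there only the direction is unlabelled. The point is still worth correcting, because the trial's main decision rule should not depend on an unstated program option.

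**What to change.** State in SAP 1.8.2 and 2.2.2 that PASI 90 response is the modelled event, then choose one option:

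- **(a)** Use 6-weekly as the reference in the primary model, or request the 4-weekly versus 6-weekly contrast. Keep β0 = +ln(2.23), take a lower-tail one-sided p-value, and require the upper 95% limit of OR(4w/6w) not to exceed 2.23.
- **(b)** Keep 4-weekly as the reference. Set β0 = −ln(2.23), take an upper-tail one-sided p-value, and require the lower 95% limit of OR(6w/4w) to be at least 1/2.23 = 0.448.

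The two options are equivalent. Name the chosen direction in SAP 1.8.6, use it in the per-protocol and multiple-imputation repeats, and label the comparison on the outputs. The key secondary model can keep 4-weekly as reference. The cost is two or three SAP sentences and one or two program options, with no change to data or design.
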